3.3.4.1 Withdrawal of consent to participation

Patients may withdraw their consent to participation at any time without the need to justify the decision.

If a patient wants to withdraw consent, the investigator should be involved in the discussion with the patient and the options for continued follow-up after discontinuation of remote monitoring and other study procedures.

3.3.4.2 Discontinuation of the study by the contracting entity

Boehringer Ingelheim reserves the right to discontinue the study overall or at a particular study site at any time for the following reasons:

- 1. Failure to meet expected enrolment goals overall or at a particular study site.
- 2. New safety information invalidating the earlier positive benefit-risk-assessment, please see Section 1.4.
- 3. Deviations from GCP, the study protocol, or the contract impairing the appropriate conduct of the study.

Further assessment and follow up of patients affected will occur as described in Section 3.3.4.1.

The investigator / the study site will be reimbursed for reasonable expenses incurred in case of study termination (except in case of the third reason).

Page 23 of 71

Proprietary confidential information © 2022 Boehringer Ingelheim International GmbH or one or more of its affiliated companies

4. **TREATMENTS**

4.1 INVESTIGATIONAL INTERVENTION

The cough monitor will be worn by all study participants over 4 24-hour recordings during the 12-week study period. No investigational medicinal product will be administered. Please see Section 1.2.

4.1.1 Method of assigning patients to intervention group

All enrolled subjects will receive the intervention of utilizing a wearable cough monitoring device with an accompanying mobile application (App) for data. All enrolled subjects will also receive a home spirometry device and accompanying mobile application and study provisioned smart phone (for the study duration).

4.1.2 Storage conditions

The sensor and charger are provided to the patient with custom packaging. This hardware can be stored and transported within standard environmental conditions (-25°C to 50°C, 15% to 93% RH \pm 3%, 700hPa to 1,070hPa). When not in use and between measurements the patient can store the wearable device on the charger. The charger was designed to fit within a small footprint on a table or desktop.

4.1.3 Device accountability

The investigator or designee will receive the system kit, as delivered by the contracting entity or delegate when the following requirements are fulfilled:

- Approval of the study protocol by the IRB / ethics committee and/or HA approval
- Availability of a signed and dated study protocol contract between the contracting entity contracting entity or delegate and the investigational site,
- Approval / notification of the regulatory authority, e.g. competent authority,
- Availability of the curriculum vitae of the Principal Investigator,
- Availability of a signed and dated study protocol,
- Availability of the proof of a medical license for the Principal Investigator,
- Availability of FDA Form 1572 (if applicable).

Investigational devices are not allowed to be used outside the context of this protocol. They must not be forwarded to other investigators or clinics. Patients should be instructed to return unused devices and/or devices upon study completion.

The investigator or designee must maintain records of the product's delivery to the study site, the inventory at the site, the use by each patient, and the return to the contracting entity of unused products.

These records will include dates, quantities, batch / serial numbers, expiry ('use- by') dates, and the unique code numbers assigned to the study patients. The investigator or designee will maintain records that document adequately that the patients were provided the device(s) specified by the study protocol. At the time of return to the contracting entity the investigator

or designee must verify that all unused supplies have been returned by the study protocol patient and that no remaining supplies are in the investigator's possession.

4.2 OTHER TREATMENTS, EMERGENCY PROCEDURES, RESTRICTIONS

4.2.1 Other treatments and emergency procedures

There are no special emergency procedures to be followed.

4.2.2 Restrictions

4.2.2.1 Restrictions regarding concomitant treatment

As per the Exclusion criteria (3.3.3), persons who have had initiation of a change in dose of ACE-I therapy, inhaled steroid therapy (excluding intranasal), systemic corticosteroid, antitussive therapy (including over the counter medications) or opiate therapy within 4 weeks of study entry are not eligible for inclusion. If a patient experiences a clinical deterioration requiring initiation of or a change in dose of one of the aforementioned classes of medication during the study period, the site principal investigator must notify the contracting entity within 72 hours.

4.2.2.2 Restrictions on lifestyle

Patients can perform most forms of exercise, typical daily activities and shower while wearing the device. Full submersion into water (e.g. swimming, hot tub use or baths) is not advised as it may lead to device malfunction and compromise any further data collection.

4.2.2.3 Contraception requirements

No contraception requirements are necessitated by use of the device.

4.3 **DEVICE USE COMPLIANCE**

Compliance with cough recordings will be assessed based on patient adherence to cough monitoring (defined as % of time over the 24-hour recording period that the patient is wearing the cough monitor) and remote cough data capture (defined as % of analyzable data per 24-hour recording).

Site staff will receive notification via email each time a patient completes a cough count recording with successful data upload. If the site does not receives this type of notification, the site should contact the patient to assess whether the patient requires assistance with any elements of the 24 hour cough recording and upload.

Page 25 of 71

Proprietary confidential information © 2022 Boehringer Ingelheim International GmbH or one or more of its affiliated companies

5. ASSESSMENTS

Subjects will complete 7 study visits (Figure 3.1: 1), 3 on site and 4 remotely. At the Screening Visit (V1), demographic information, pregnancy status (where available), medical history, ILD diagnosis category, HRCT pattern (most recent study within previous 12 months), presence or absence of progressive pulmonary fibrosis phenotype, active medications (related to Non-IPF Pulmonary Fibrosis or IPF and unrelated concomitant medications), and historical FVC and DLCO (within the prior 12-month period) will be recorded into the EDC by the on-site study team. At the baseline visit (V2), which can occur on the same day as the Screening visit,

a physical exam including vital signs will be performed, and blood will be drawn At V2, patients will be given a cough monitor system kit, instructed on use and supervised to self-apply the biosensor to their chest wall and turn on the 24-hour recording setting. Patients will also be given a home spirometer at the baseline visit. They will receive an introduction to the home spirometry device and platform and instruction on use of the home spirometer.

5.1 ASSESSMENT OF EFFICACY

No medical therapeutic intervention will be administered. Accordingly, no primary efficacy analyses will be performed in this low intervention pilot study. However, measures of cough frequency and FVC will be integral to the primary and secondary outcome analyses; descriptions are included below. Cough intensity will also be examined in exploratory analyses.

Cough Severity

Cough severity will be evaluated based on both a) cough frequency – measured as 24-hour log-transformed cough count and b) cough intensity. The formed monitor utilizes a proprietary algorithm to analyze 24 hour or periodic recordings for respiratory and cough sounds. Four 24-hour cough recordings will be performed over the course of the 12-week pilot study. Data will be uploaded via Bluetooth interface from the formed biosensor to the formed Mobile App and subsequently from the formed Mobile App to the Cloud. Both artificial intelligence driven cough data analyses as well as cough reports in which audio and spectrographic recordings are manually overread will be available.

FVC

On-site spirometry measurements will be performed according to ATS/ERS 2019 guideline [R20-2419]. FVC will be assessed using standardised spirometry equipment which will be provided centrally with supplies of precalibrated disposable flow sensors. These sensors meet International Organization for Standardization (ISO) 26782 standards, but with a maximum permissible accuracy error of $\pm 2.5\%$, in accordance with the American Thoracic Society (ATS)/European Respiratory Society (ERS) Technical Statement [R20-2419]. As such there is no need to conduct daily calibration prior to use. Only these spirometers are to be used for this study.

Spirometry will be conducted with the patient in a seated position. It is preferable that the same trained individual performs the PFTs for a given patient. The best of three efforts will be defined as the highest FVC obtained on any of three blows meeting the 2019 ATS/ERS criteria (with a maximum of eight attempts). Predicted normal values will be calculated according to GLI (Global Lung Initiative). Efforts should be made to schedule the spirometric measurements at approximately the same time of the day, at least within the same half-day (morning vs afternoon), with reference to baseline measurement (Visit 2). On days of study visits, patients should be encouraged to refrain from vigorous activity within 1 hour of pulmonary function testing. If treated with bronchodilators, washout should be advised before spirometry and documented in source documents. If treated with bronchodilators should be observed before spirometry and documented in source. Spirometry results will be electronically transmitted. To ensure the quality of the spirometry measures, a manual overread will be performed by the spirometry vendor. Further instructions regarding FVC measurements will be provided in the ISF.

Video supervised home spirometry measurements will be performed. Patients will receive instruction on the video supervised home spirometer use at the Baseline Visit (V2). The first "home spirometry" measure will be performed at home two days following the baseline study visit (with study coordinator instruction and video assisted supervision). Patients will also perform video supervised home spirometry measurements at remote Visits 4, 5, and 6. For the video-assisted home spirometry, patients will use a handheld spirometer together with a mobile phone with the installed App provided by site. These home spirometry measurements at Visit 2 and Visit 7 (Week 12).

Page 28 of 71

Proprietary confidential information © 2022 Boehringer Ingelheim International GmbH or one or more of its affiliated companies

Biosensor

As noted in Section 1.2, the **B**iosensor will be used to capture 24-hour recordings of cough frequency data. Additionally, data acquired in this study using the cough monitor might be analyzed further to e.g. build diagnostic, prognostic and predictive models and develop new algorithms for the analysis of cough data. This exploratory analysis might be performed in collaboration with an independent third party nominated by the contracting entity.

5.2 ASSESSMENT OF SAFETY

5.2.1 Physical examination

A complete physical examination will be performed at Visit 2 and 7, as specified in the Flow Chart. It includes at a minimum general appearance, neck, lungs, cardiovascular system, abdomen, extremities, and skin. Measurement of height and body weight will be performed at Visit 2 and 7. The results must be included in the source documents.

16 Sep 2022

Protocol

Proprietary confidential information © 2022 Boehringer Ingelheim International GmbH or one or more of its affiliated companies

5.2.2 Vital signs

Vital signs will be evaluated at Visit 2 and 7, as specified in the Flow Chart, prior to blood sampling. This includes systolic and diastolic blood pressure and pulse rate (electronically or by palpation count for 1 minute) in a seated position after 5 minutes of rest. The results must be included in the source documents.

5.2.3 Safety laboratory parameters

Safety laboratory parameters will not be performed.

5.2.4 Electrocardiogram

ECGs will not be routinely performed.

5.2.5 Other safety parameters

Should the patient demonstrate $a \ge 10\%$ absolute or relative drop in forced vital capacity (FVC) during on-site or home spirometry, the site principal investigator will be notified and asked to assess whether any further evaluations are needed.

5.2.6 Assessment of adverse events

5.2.6.1 Definitions of AEs

5.2.6.1.1 Adverse event

An AE is defined as any untoward medical occurrence in a patient or clinical investigation subject administered a medical intervention and which does not necessarily have to have a causal relationship with this Intervention.

An AE can therefore be any unfavourable and unintended sign (including an abnormal laboratory finding), symptom, or disease temporally associated with the use of a medical intervention, whether considered related or not.

The following should be recorded as an AE in the CRF (if applicable):

- AEs related to study procedures
- AEs or SAEs that fufill the following criteria:
 - Events leading to lung transplantation
 - COVID-19 Infection
 - o Events leading to death

5.2.6.1.2 Serious adverse event

A serious adverse event (SAE), is defined as any AE, which fulfils at least one of the following criteria:

• results in death

- is life-threatening, which refers to an event in which the patient was at risk of death at the time of the event; it does not refer to an event that hypothetically might have caused death if more severe,
- requires inpatient hospitalisation or prolongation of existing hospitalisation
- results in persistent or significant disability or incapacity,
- is a congenital anomaly / birth defect,
- is deemed serious for any other reason if it is an important medical event when based on appropriate medical judgement which may jeopardise the patient and may require medial or surgical intervention to prevent one of the other outcomes listed in the above definitions. Examples of such events are intensive treatment in an emergency room or at home for allergic bronchospasm, blood dyscrasias or convulsions that do not result in hospitalisation or development of dependency or abuse.

SAEs related to study procedures, or as defined in Section 5.2.6.1.1, should be recorded in the CRF.

No SAE reporting to drug safety will occur, hence no SAE reconciliation required.

5.2.6.1.3 AEs considered "Always Serious"

Not applicable

5.2.6.1.4 Adverse Events of Special Interest

Not applicable

5.2.6.2 Adverse event collection and reporting

5.2.6.2.1 AE Collection

The investigator shall maintain and keep detailed records of all AEs in the patient files.

The following must be collected and documented on the appropriate CRF(s) by the investigator:

• From signing the informed consent onwards until the individual patient's end of study (= the End of Study (EoS) visit): all AEs (serious and non-serious) as defined in Section 5.2.6.1.1.

5.2.6.2.2 AE reporting to the contracting entity and timelines

Not applicable

5.2.6.2.3 Exemptions to SAE reporting

Not applicable

Page 31 of 71

Proprietary confidential information © 2022 Boehringer Ingelheim International GmbH or one or more of its affiliated companies

5.4 BIOBANKING

Not applicable

5.5 OTHER ASSESSMENTS

Resource use data will include unscheduled hospitalizations, healthcare provider visits, and emergency room use.

5.6 APPROPRIATENESS OF MEASUREMENTS

Cough count or frequency of cough is a standard and routine measure utilized in studies of anti-tussive therapy. In the current pilot, we will also measure, "cough intensity", which is not routinely captured by current cough monitors. As such, it is not a measure that is routinely included in published literature to date. In the current study, we will assess cough

intensity, measured as an analysis of a combination of the following parameters: cough duration (% of minute recordings taken up by cough), variability of minute-to-minute cough%/minute, time interval of coughs (msec) on x axis, amplitude of cough on y-axis, AUC of cough per cough or cough spasm, and within cough power (measured by color - clear, blue, yellow, red; worst color present and change in color over time).

Page 33 of 71

Proprietary confidential information © 2022 Boehringer Ingelheim International GmbH or one or more of its affiliated companies

6. INVESTIGATIONAL PLAN

6.1 VISIT SCHEDULE

A multi-center, real-world low intervention pilot study based on newly collected data from approximately 50 evaluable subjects with Non IPF Pulmonary Fibrosis and IPF will be conducted in various sites in the North America and Europe.

The eligible subjects will be identified by the participating specialist physicians including pneumologists involved in the diagnosis, treatment, and management of Non IPF Pulmonary Fibrosis or IPF. The participant selection process will be consecutive, and the participating specialist physicians will be provided guidance to minimize any potential selection bias. Eligible subjects must be previously diagnosed with Non IPF pulmonary fibrosis or IPF and will be asked to provide written informed consent prior to inclusion in the study.

Consenting subjects will be followed for a maximum period of 12 weeks (Figure 3.1: 1); all subjects will participate in 7 clinical visits, 3 in person and 4 remote visits.

During the screening visit (V1) and the baseline visit (V2), baseline data will be collected, including on-site spirometry, historical HRCT pattern (most recent study within the previous 12 months), historical FVC% (most recent value within 6 months prior to V2 & most distant value within 12 mos. of V2), DLCO% predicted (most recent value within 6 months prior to V2 & most distant value within 12 mos of V2),

Where allowed by local regulations, a subject screening log will be kept at each site, recording basic information such as age at Non IPF Pulmonary Fibrosis or IPF diagnosis, sex, information on the eligibility (or reasons for non-eligibility/non-enrollment, including a reason for refusal [if known]) and the study (i.e. having provided informed consent) will be maintained in the Investigator Site File (ISF).

Subjects will be followed prospectively from the time of enrollment until the earliest of death, loss to follow-up or end of the study period. Subjects who are alive and not lost to follow-up, will complete their study participation once study procedures have been completed for Visit 7.

If a patient misses a visit, the site is asked to alert the contracting entity to determine if the visit should be rescheduled. Subjects are free to discontinue or withdraw from the study at any time. Reason for discontinuation or withdrawal will be collected; however, reasons for withdrawal of consent do not have to be disclosed. Unless otherwise requested by the participant, all data obtained up to consent withdrawal will be retained in the database.

Screening Period (Visit 1)

- Following provision of informed consent, Inclusion & Exclusion criteria should be reviewed as per the FC
- During the screening visit, demographic information will be collected.
 - Age on the day of informed consent (in years)

- Sex (male, female; to describe the patient's sex at birth)
- Ethnicity and race in order to sufficiently characterize the patient population, to support possible subgroup analyses if needed unless not acceptable according to local regulations.
- Medical history (Comorbidities, COVID-19 infection history and vaccination status)
- Pregnancy status (where available)
- Non IPF pulmonary fibrosis (including ILD diagnosis category) or IPF Diagnosis
- Presence or absence of progressive pulmonary fibrosis (PPF) phenotype
- Smoking status/history
- Concomitant medications
- HRCT pattern (most recent study within previous 12 months)
- FVC & DLCO (most recent value within 6 months prior to V2 & most distant value within 12 months of V2)

Visit 2/Baseline Visit – On site

The Screening Visit and Baseline Visit can occur on the same day.

Vital signs will be taken, and a physical exam performed. Subsequently, a pulmonary function test will be performed to measure FVC.

Instructions for utilizing and storing the cough monitor will be reviewed. The patient will place the biosensor onto their chest wall with supervision and assistance (as needed) from the study team. The sensor will be set and started on recording mode for the planned 24hrs. recording. At completion of 24hrs. of recording the next day, the patient will place the charger to allow for data upload via Bluetooth connected app on the study-provided mobile phone. The sensor will be charged for the next visit and stored as per vendor instructions until the next recording at Visit 4. At Visit 2, patients will additionally receive a home spirometer and instructions for use will be reviewed with the patient including access to the video assist portal on the provisioned mobile phone for study use.

Visit 3- Remote

On Day 3 of the study (+ 2 days) the patient is asked to complete home spirometry (Visit 3) via video-assisted supervision by a trained member of the site study team.

Visit 4 - Remote

Visit 4 (V4) will occur on the 28th day (+/- 5 days) after study enrollment/baseline visit. Visit 4 will be fully remote.

Page 35 of 71

Proprietary confidential information © 2022 Boehringer Ingelheim International GmbH or one or more of its affiliated companies

On the day of the visit, the participant will logon to the platform for a videoconference visit with the site study team preceding home spirometry.

Subsequently, interval history will be obtained, followed by video-assisted supervised home spirometry with the site study team. Immediately following the end of the study visit, the patient will initiate a 24-hour cough recording. At completion of 24 hrs. of recording the next day, the patient will remove the sensor from their chest wall and place the sensor onto a charger to allow for data upload via Bluetooth connected app on the study-provided mobile phone. The charger will be placed next to the study provided mobile phone, which is "pre-loaded" with the sensor for data upload.

The sensor will be charged for the next visit and stored as per vendor instructions until the next recording at Visit 5.

Visit 5 - Remote

Visit 5 (V5) will occur on the 56th day (+/- 5 days) after study enrollment/baseline visit. Visit 5 will be fully remote.

On the day of the visit, the participant will logon to the platform for a videoconference visit with the site study team preceding home spirometry.

Subsequently, interval history will be obtained, followed by video-assisted supervised home spirometry with the site study team. Immediately following the end of the study visit, the patient will initiate a 24-hour cough count recording. At completion of 24 hrs. of recording the next day, the patient will remove the sensor from their chest wall and place the sensor onto a charger to allow for data upload via Bluetooth connected app on the study-provided mobile phone. The charger will be placed next to the study provided mobile phone, which is "pre-loaded" with the place app, to allow for data upload. The sensor will be charged for the next visit and stored as per vendor instructions until the next recording at Visit 6. The site study team will confirm that the prior 24-hour cough recording was completed and offer to assist the patients with any part of the 24-hour cough recording that they were having trouble with.

Visit 6- Remote

Visit 6 will occur on the 82nd day (-2 days) prior to the EoS visit. On the day of the study visit, the patient is asked to complete home spirometry (Visit 6) via logon to the platform for video supervision by a spirometry trained member of the site study team. Immediately following the end of the study visit, the patient will initiate a 24-hour cough recording. At completion of 24 hrs. of recording the next day, the patient will remove the sensor from their chest wall and place the sensor onto a charger to allow for data upload via Bluetooth connected app on the study-provided mobile phone. The charger will be placed next to the study provided mobile phone, which is "pre-loaded" with the provided app,

Proprietary confidential information © 2022 Boehringer Ingelheim International GmbH or one or more of its affiliated companies

to allow for data upload. Once data upload is complete, the sensor and study provided phone will be stored for return to the site at the EoS visit (Visit 7).

Visit 7 – On site

The End of Study Visit (EoS/V7) will occur on the 84th day (+/- 5 days) following study enrollment/baseline visit.

Interval history will

be obtained; vital signs and a physical exam will be performed. Participants will then undergo spirometry on-site.

The and home spirometry devices will be returned to the site as will the provisioned mobile phone.

In the event of force majeure or other disruptive circumstances (e.g. pandemic, war) the investigational plan as per this study protocol may not be feasible at a site. With the consent of the patient, contracting entity and investigator may agree on alternative, back-up or rescue methodology which may include but will not be limited to virtual patient visits and assessments and home healthcare nurse visits.

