1.3 RATIONALE FOR PERFORMING THE STUDY

As highlighted, significant gaps in knowledge remain regarding etiology of cough, consequences of cough and appropriate treatment of cough in patients with pulmonary fibrosis. A further understanding of the similarities and differences in cough among persons with Non IPF Pulmonary Fibrosis and IPF, together with insight into the pattern and impact of cough in these patients is required.

The current pilot aims to assess cough frequency, indirect measures of cough intensity and the association between objective cough measures and lung physiology, a host of patient-reported outcomes and blood-based biomarkers in a patient cohort with Non IPF Pulmonary Fibrosis or IPF. This study aims to expand the understanding of the disease and its symptoms, thereby narrowing the existing gap in knowledge, and to help support the development of future compounds targeting cough.

We will utilize a hybrid study design in which 4 visits will be conducted remotely and all cough data will be captured via a wearable, digitally enabled cough monitor with bluetooth capabilities that allow secure remote upload. Furthermore, patients will perform video-assisted home spirometry. The intention of incorporating 4 remote visits into the study design is to assess the potential to ease the burden of study procedures on patients and physicians, thereby broadening the subject pool to those who might otherwise not have access to enroll in this pilot. If successful, this type of study design could also be employed in Phase 2 and 3 interventional trials and allow a broader and more racially, geographically, and socioeconomically diverse patient population access to clinical trials.

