2.1 MAIN OBJECTIVES, PRIMARY AND SECONDARY ENDPOINTS

2.1.1 Main objectives

The primary objective of this study is to objectively describe cough frequency, utilizing four 24-hour cough recordings over 12 weeks in a cohort of subjects with Non IPF Pulmonary Fibrosis or IPF using the cough monitor.

The secondary objectives for this study are:

- Assess the relationship between objective cough frequency and FVC (mL)
- Assess feasibility of patient performed remote cough data upload
- Assess feasibility of hybrid study design (% successful completion of remote visits)

2.1.2 **Primary endpoint(s)**

Primary Endpoints: Cough count per hour (CC/hr) measured over a 24-hour period at baseline visit, Week 4(V4), Week 8(V5), Week 12 (V6).

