2.1.3 Secondary endpoint(s)

Secondary endpoints include:

- Change from baseline in CC/hr at Week 4, Week 8, Week 12.
- FVC (mL) at baseline
- FVC (mL) at Week 12
- Change from baseline in FVC (mL) at Week 12
- Feasibility of remote cough data capture (defined as % of analysable data per 24-hour recording)
- Feasibility of hybrid study design (successful completion of all elements of remote visit)

 406431-01
 Protocol
 Page 17 of 71

 Proprietary confidential information © 2022 Boehringer Ingelheim International GmbH or one or more of its affiliated companies
 Proprietary Confidential information © 2022 Boehringer Ingelheim International GmbH or one or more of its affiliated companies

 406431-01
 Protocol
 Page 18 of 71

 Proprietary confidential information © 2022 Boehringer Ingelheim International GmbH or one or more of its affiliated companies
 Proprietary Confidential information © 2022 Boehringer Ingelheim International GmbH or one or more of its affiliated companies

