The % of analysable data per 24-hour recording period will be derived from the cough count recording times(Total readable recording time) and defined as:

Total readable recording time

24 (hours)

- x 100

Descriptive statistics will be produced by visit as well as the number and percentage of patients who have $\geq 80\%$ (19.2 hrs) of analyzable data.

• Feasibility of hybrid study design (successful completion of all elements of remote visit)

Successful completion of a remote visit will be based on the questions on the home study procedures eCRF:

- Was home spirometry performed? (Visit 3, Visit 4, Visit 5, Visit 6)
- Was the videoconference televisit completed? (Visit 4, Visit 5)
- Was the 24 hour cough recording completed? (Visit 3, Visit 4, Visit 5)

The number and percentage of patients who complete each element will be tabulated by visit as well as the number an percentage of patients who complete all elements by visit.

Correlation analyses:

Sample Spearman and Pearson correlation coefficients for the pairs of CC/hr and FVC measurements listed above along with the associated p-values to assess the relationship between objective cough frequency and FVC (mL), correlations will be calculated. Scatter plots for the pairs of variables will also be produced.

Boehringer Ingelheim

 TSAP for BI Trial No: 1490-0005
 Page 19 of 27

 Proprietary confidential information © 2024 Boehringer Ingelheim International GmbH or one or more of its affiliated companies

001-MCS-50-415_RD-01 (3.0) / Saved on 18 Jan 2021

Boehringer Ingelheim TSAP for BI Trial No: 1490-0005

Proprietary confidential information © 2024 Boehringer Ingelheim International GmbH or one or more of its affiliated companies

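### Hybrid feasibility is scored as completed at any time, so a remote visit made up late or done outside its window cannot be told apart from one done on schedule

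*Protocol*

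**What the plan says.** **Objective and endpoint.** Protocol 2.1.1 lists as a secondary objective: "Assess feasibility of hybrid study design (% successful completion of remote visits". Protocol 2.1.3 gives the endpoint: "Feasibility of hybrid study design (successful completion of all elements of remote visit". Neither mentions timing. Protocol 1.3 states the use to which the result may be put: "If successful, this type of study design could also be employed in Phase 2 and 3 interventional trials".

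**Schedule.** Protocol 6.1 sets the Visit 4 window: "Visit 4 (V4) will occur on the 28th day (+/- 5 days) after study enrollment/baseline visit". By the flow chart, Visit 3 is day 3 (+2 days), Visit 5 is day 56 (±5 days) and Visit 6 is day 82 (−2 days).

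**Missed visits.** Protocol 6.1: "If a patient misses a visit, the site is asked to alert the contracting entity to determine if the visit should be rescheduled". The decision is made case by case.

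**Scoring.** SAP 7.5.2: "Successful completion of a remote visit will be based on the questions on the home study procedures eCRF". The questions are "Was home spirometry performed? (Visit 3, Visit 4, Visit 5, Visit 6", "Was the videoconference televisit completed? (Visit 4, Visit 5" and a third on whether the 24-hour cough recording was completed, listed for Visits 3, 4 and 5. Each element, and all elements together, are tabulated by visit. No date enters.

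**Set and denominator.** The Entered Set is used (SAP 6.3). By default, percentages are taken over all subjects in the set, with or without data (SAP 7).

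**The concern.** The protocol gives every remote visit a window, but the measure of whether remote visits work does not use it. A visit done on day 28 and the same visit made up well after its window closed both yield a yes to each question. The planned table therefore mixes two things: whether patients and technology delivered the visit when it was due, and whether it could be obtained in the end, which depends partly on how often rescheduling was agreed. Anyone using this pilot to plan a later trial would probably want the two separately, and the planned output cannot supply them.

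**Working it through.** **Step 1. The plan's own figure.** None is given for feasibility: no expected completion rate, late rate or success threshold. The only sizing figure is the confidence-interval half-width for mean cough count (Protocol 7.5). It reproduces, 1.960 × 27 / √50 = 7.484, but has no bearing here.

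**Step 2. Four kinds of visit run through the SAP 7.5.2 scoring.**

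| Remote visit | Protocol window | Score |
|---|---|---|
| Done as first planned | inside | completed |
| Rescheduled, still inside the window | inside | completed |
| Missed and made up late, or simply done late or early | outside | completed |
| Never done | – | not completed; stays in the denominator |

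Only the third row is a problem: it cannot be distinguished from the first two.

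**Step 3. Do the SAP 6.7 windows supply the check?**

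| Visit | Protocol days | SAP 6.7 days |
|---|---|---|
| 3 | 3 to 5 | 2 to 16 |
| 4 | 28 ± 5 = 23 to 33 | from 29 − 12 = 17; end not legible in the text available |
| 5 | 56 ± 5 = 51 to 61 | from 57 − 13 = 44; end not legible |
| 6 | 80 to 82 | from 71 to the day before the last in-office visit |

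The SAP windows for Visits 3 and 6 are wider than the protocol's, and those for Visits 4 and 5 open earlier. For example, a Visit 4 done 10 days late falls on day 38. That is 5 days past the protocol limit of 33 and before the Visit 5 window opens on day 44, so it could still be labelled Visit 4. SAP 6.6 defines one approach that ignores time windows and one that applies the SAP windows. The visible text does not say which governs feasibility. Neither uses the protocol windows.

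**Step 4. Size.** Let C be the patients who ever completed a given visit, k those of them who did so outside the protocol window, and N = 50 (the planned total). Ever completed is C/N and on-schedule is (C − k)/N, so the gap is k/N = k/50, or 2.0 percentage points per late visit. The values of C and k below are assumptions; intervals are Wilson 95%.

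| k | C = 45: on-schedule rate | C = 40: on-schedule rate |
|---|---|---|
| 0 | 90% (78.6–95.7) | 80% (67.0–88.8) |
| 1 | 88% (76.2–94.4) | 78% (64.8–87.2) |
| 3 | 84% (71.5–91.7) | 74% (60.4–84.1) |
| 5 | 80% (67.0–88.8) | 70% (56.2–80.9) |
| 10 | 70% (56.2–80.9) | 60% (46.2–72.4) |

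With k = 0 the two rates coincide.

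**The case against.** The strongest reply is that the endpoint is completion, and the SAP implements it faithfully. Neither the objective nor the endpoint mentions timing, so the reported rate is correct for what it claims to be. No passage says that remote visits in later trials must fall on schedule. Protocol 1.3 speaks of easing burden and widening access, and a visit obtained after rearrangement fits that aim. The study is exploratory with no hypotheses (Protocol 7.1) and has no feasibility threshold, so no decision rule changes. Timing is not wholly hidden either: departures from the protocol are treated as deviations (Protocol 8), important ones are handled under SAP 6.2, and all individual data are to be listed (Protocol 7.2.1).

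Most of this stands, and it rules out redefining the endpoint. It does not answer the narrower point. In a descriptive pilot the summary table is the result, and neither listings nor a deviation process give a by-visit rate of on-schedule completion.

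Two stronger readings are tempting and fail:
- A reader might infer that missed visits score as successes. They do not: a visit never done is a no and stays in the denominator by default.
- A reader might infer that every rescheduled visit is off schedule. A Visit 4 moved from day 27 to day 30 is still inside the ±5-day window. Counting it as a failure would be stricter than the protocol.

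**Conclusion.** The point holds in a limited form. SAP 7.5.2 cannot separate on-schedule completion from eventual completion, and the SAP 6.7 windows do not help. The planned rate is right as a rate of visits ever completed and would overstate feasibility only if read as on-schedule completion. The gap is 2 percentage points per out-of-window visit with N = 50. Its total is unknown and may be zero.

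A reader might go further and conclude that feasibility is overstated, perhaps by assuming a miss rate and a recovery rate and multiplying over the four remote visits. The documents do not support that. They give neither rate, the SAP plans no all-visits composite, and independence between a patient's visits would be a further assumption.

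The conclusion rests on the visible SAP text and on N = 50; an Entered Set of another size changes the points per visit to 100/N. The primary endpoint is unaffected. This is a cheap improvement to one secondary endpoint, not a flaw that undermines the study.

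**What to change.** In SAP 7.5.2, keep the completion endpoint as it is. Add, for each remote visit, the number and percentage of patients in three categories:
- all elements completed within the protocol flow-chart window;
- all elements completed, but at least one outside that window;
- not all elements completed.

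The first two add up to the planned rate. A visit rescheduled inside the window counts as within window. Report the number rescheduled only where it was recorded; the documents do not show a flag being collected. State which SAP 6.6 approach applies to this endpoint.

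Two matters must be reconciled before programming:
- **Day numbering.** The flow chart puts Visits 4, 5 and 6 on days 28, 56 and 82. SAP 6.7 puts them on days 29, 57 and 83. Both call baseline day 1.
- **Recording element.** SAP 7.5.2 lists the cough recording for Visits 3, 4 and 5, whereas the flow chart schedules recordings at Visits 2, 4, 5 and 6. Read literally, all elements at Visit 6 means home spirometry alone, and Visit 3 asks for a recording not scheduled there.

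**Cost.** One extra derived table and a few lines of SAP text. Visit dates are already among the source data for the CRF (Protocol 8.3.1), so the window split needs no new collection. The drawback is an on-schedule figure that may be less favourable than the any-time figure beside it.
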